6.2.2. Concomitant Medications

In cases of a missing start or end date, the following methods will be implemented:

Missing start date:

- Missing entire date: estimate the date of DEFINITY® administration
- Missing day and month:
 - If the year is the same as the year of the DEFINITY® administration date, it will be estimated by the date of DEFINITY® administration
 - If the year is different to the year of the DEFINITY® administration date, it will be estimated as 1st January of that year
- Missing day only:
 - If the month/year are the same as the month/year of the DEFINITY® administration date, it will be estimated by the date of DEFINITY® administration
 - If the month/year is different to the month/year of the DEFINITY® administration date, it will be estimated as the first day of the month

Missing end date:

- Missing entire date: estimate the End of Study date
- Missing day and month:
 - If the year is the same as the year of the End of Study date, it will be estimated by End of Study date
 - If the year is prior to the year of End of Study date, it will be estimated by as 31st December of that year
- Missing day only:
 - If the month/year are the same as the month/year of End of Study date, it will be estimated by the End of Study date
 - If the year or month is different from the year or month of End of Study date, it will be estimated by the last day of the month

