5.6 Concomitant Therapy

Concomitant medications will be collected from the screening visit to the 72 ± 24 hour safety follow-up phone call, and will be recorded on the eCRF.

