7.4.1. Prior Medication

Prior medications are those that started and stopped before exposure to DEFINITY®.

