7.4.2. Concomitant Medication

Concomitant medications are all medications taken during the study period, including those which started before administration, but were reported ongoing at the first administration.

This document is confidential.

8. Efficacy

All efficacy parameters will be summarized and presented in tables based on the mITT and PP populations. Note, approximately 10% of imaging scans will be re-read by each reader. Unless otherwise specified, the first/original read is what will be used for all reporting and statistical analyses.

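### The medication start-date rule in SAP 6.2.2 ignores a known stop date, and the prior and concomitant classes in SAP 7.4 are not clearly exclusive

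*SAP*

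**What the plan says.** SAP 6.2.2 sets a missing start to the dosing date in three situations:

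- No date at all: "Missing entire date: estimate the date of DEFINITY® administration".
- Day and month missing: "If the year is the same as the year of the DEFINITY® administration date, it will be estimated by the date of DEFINITY® administration".
- Day missing: "If the month/year are the same as the month/year of the DEFINITY® administration date, it will be estimated by the date" of administration.

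If the known year or month differs from that of dosing, the start becomes 1 January of that year or, where only the day is missing, "it will be estimated as the first day of the month". No branch refers to the stop date, and nothing says what to do when the start ends up later than the stop.

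SAP 7.4 plans separate prior and concomitant tables and listings for the Safety Population and points to 6.2.2 for records with missing data. SAP 7.4.1 says: "Prior medications are those that started and stopped before exposure to DEFINITY". SAP 7.4.2 says: "Concomitant medications are all medications taken during the study period, including those which started before administration, but were reported ongoing at the first administration". The SAP does not define the study period. Protocol 5.6 gives the collection window: "Concomitant medications will be collected from the screening visit to the 72 ± 24 hour safety follow-up phone call". Under Protocol 6.1 and SAP 3.8.1, screening may be up to 7 days before dosing.

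SAP 6.2.3, on adverse events, moves an incomplete start date to the dosing day only when the available information cannot settle whether the event came before dosing.

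**The concern.** Assigning an unknown start to the dosing day is a sensible cautious default when the timing really is unknown. It is not cautious when the record itself shows that the drug ended before dosing. The rule then creates an impossible pair of dates and changes the drug's class. The adverse event rule in the next section applies the right logic; the medication rule does not.

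The second problem is that the two classes use different reference points. Prior is defined against exposure, concomitant against a period whose start is not given. Two programmers working from the same SAP could produce different tables.

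At stake is whether the two tables correctly separate drugs already stopped from drugs in use when DEFINITY was given. SAP 4.3 includes changes in concomitant medication in the safety follow-up. Protocol 6.3 has medication data taken by interview and record review, where incomplete dates are to be expected.

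**Working it through.** The plan gives no figure to reproduce, so the check applies the rules literally.

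**Inputs.** Let D be the dosing date, E the recorded stop date and S the start date used. The imputation rule is from SAP 6.2.2, the class definitions from SAP 7.4.1 and 7.4.2, and the 7-day window from SAP 3.8.1.

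**Step 1: date order.** In the three branches, S = D. If E < D, then S − E = D − E > 0, so the start always falls after the stop. Enumerating the day-missing branch over every 2018 dosing day and every earlier stop day in the same month confirms this. A month of d days has d(d − 1)/2 such pairs: 7 × 465 + 4 × 435 + 378 = 3255 + 1740 + 378 = 5373, and all 5373 give a start after the stop. This restates the rule; it says nothing about how often such records occur.

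**Step 2: the prior class.** Prior requires S < D and E < D. With S = D the first condition fails, whatever E is.

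**Step 3: examples.** Assume dosing on 20 November 2018 and screening on 13 November 2018, 7 days earlier.

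| Record | Start used | Prior | Concomitant, if study period runs from screening | Concomitant, if study period runs from dosing |
|---|---|---|---|---|
| Start unknown, stop 18 Nov | 20 Nov | No | Yes | Yes if the imputed start decides; no if the stop decides |
| Start 14 Nov, stop 18 Nov, complete | 14 Nov | Yes | Yes | No |
| Start October, day missing, stop 10 Nov | 1 Oct | Yes | No | No |

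In row 1 the imputed start is 20 − 18 = 2 days after the stop. A drug that stopped on 18 November must have started by then, so it did start and stop before dosing, yet it fails the prior definition. Under the dosing reading it ends up either concomitant or in neither class. Row 2 involves no imputation and shows the overlap: both definitions are met under the screening reading. Row 3 shows that the different-month branch works as intended.

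**Step 4: conflict within 6.2.2.** Take dosing in November, a wholly missing start, and a stop recorded only as March of that year, with the End of Study date in a later month. The end-date rule gives 31 March and the start-date rule gives the November dosing date. Both dates come from the same section, and they contradict each other.

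**The case against.** The best reply is that this is an edge case in descriptive output. Protocol 5.6 collects concomitant medication from screening, at most 7 days before dosing, and nothing requires sites to record drugs stopped earlier. Within that window, the affected records are drugs stopped in a short gap that also have an incomplete start in one of three branches. This stands as a limit on size. It does not remove the defect, because SAP 7.4 plans a prior-medication table, which can only be filled by records with a stop before dosing.

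A second reply is that the two parts interact. If the study period starts at screening, a drug stopped between screening and dosing belongs in the concomitant table whatever its start, and imputation only removes its second count as prior. If the period starts at dosing, there is no overlap. This is right, and the two harms should not be added together for the same record. Neither reading makes the rules sound: one gives double membership for fully dated drugs, the other puts a stopped drug in the wrong class or in none.

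A reader might go further in four ways that the documents do not support:

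- That drugs stopped before dosing are misclassified in general. Complete dates and the different-month and different-year branches are not affected by the imputation.
- That every affected record is wrongly counted as concomitant, or every screening-window drug counted twice. A programmer who uses only the stop date would class an affected record as prior, although that sets aside the start condition in 7.4.1. The double count depends on one reading of an undefined term.
- That listings will show negative durations. The SAP defines duration only for adverse events and does not say that imputed medication dates will be listed.
- That efficacy could be distorted. No efficacy analysis or population uses the prior/concomitant split, and both echocardiograms are done in the same subject on the same day.

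**Conclusion.** The point holds as a minor one. SAP 6.2.2 is a stated rule that gives a wrong result, not merely a missing detail: in three branches, any record with a known stop before dosing receives a start after its own stop and cannot be classed as prior. SAP 7.4 refers such records back to 6.2.2, so nothing else in the plan corrects them. The overlap between the classes is conditional. It exists if the study period starts at screening or consent, which Protocol 5.6 suggests but the SAP does not state.

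The effect is confined to the prior and concomitant medication tables and listings in the Safety Population. The documents do not allow an estimate of the number of records. The primary endpoint, the power calculation and the adverse event tables are unaffected.

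**What to change.** In SAP 6.2.2, impute the dosing date only if the stop date is missing, ongoing, or on or after the dosing date. If a known stop precedes dosing, impute a start no later than the stop; using the stop date itself is simplest. Apply the end-date rule to partial stop dates before making this check.

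In SAP 7.4, make the classes exclusive. Prior means stopped before the start of DEFINITY administration. Concomitant means ongoing at, or started on or after, the start of DEFINITY administration.

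Under these rules, row 1 of the table receives a start no later than 18 November and is prior only, row 2 is prior only, and row 3 is unchanged.

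The cost is a few sentences in the SAP and a small programming change. No new data are needed and no subject is affected.

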6.2.3. Adverse Events

If any part of the start date is missing for an AE, and it cannot be determined whether it occurred prior to the start of DEFINITY® administration, a conservative approach will be taken and the AE start date will be estimated to be the day of DEFINITY® administration.

This document is confidential.

7. Demographic, Other Baseline Characteristics and Medication

7.1. Subject Disposition

Subject disposition will include the number and percentage of ITT subjects who were enrolled in the trial, who received DEFINITY®, who completed the trial, and who discontinued from the trial. The number and percentage of ITT subjects who discontinued from the trial will also be presented by reason of discontinuation. The number and percentage of subjects in each analysis population will be presented. All percentages will be based on the total number of ITT subjects.

7.2. Demographic and Other Baseline Characteristics

All baseline and demographic characteristics will be summarized overall on the mITT. This will include age at screening, age group at screening, gender, ethnicity, race, height (cm), weight (kg), and body mass index (BMI). Descriptive statistics will be provided for each continuous variable; whereas, frequencies and percentages will be provided for categorical variables. Age, Age Group, and BMI calculations are described below:

- Age Group = two age groups will be created: (1) < 65 years, (2) ≥ 65 years
- BMI = weight(kg)/height²(m)

7.3. Medical History

Medical History will be summarized overall on the mITT population. Medical history data will be collected by body system for all enrolled subjects. The details of history by body system are collected as open text. Medical history will be coded according to Medical Dictionary for Regulatory Activities (MedDRA) version 21.0 or higher. The number and percentage of subjects within each system organ class (SOC) and preferred term (PT) will be presented. A subject experiencing a medical history within more than one SOC and PT will be counted only once within that SOC and PT, respectively.

Active medical history is defined as histories marked as ongoing at time of screening. Past medical histories are defined as histories marked as resolved at time of screening. A summary table will be provided for both active and past medical history. A listing of combined medical history will also be provided.

7.4. Medication

Medications will be coded using the World Health Organization (WHO) Drug dictionary, version Q3-2016. The number and percentage of subjects will be presented overall, by WHO therapeutic area and WHO preferred drug name. Both a table and listing will be created independently for the prior and concomitant medications for the SP. Methods for handling and categorizing missing medication data are reported in section 6.2.2.

7.4.1. Prior Medication

Prior medications are those that started and stopped before exposure to DEFINITY®.

7.4.2. Concomitant Medication

Concomitant medications are all medications taken during the study period, including those which started before administration, but were reported ongoing at the first administration.

This document is confidential.

8. Efficacy

All efficacy parameters will be summarized and presented in tables based on the mITT and PP populations. Note, approximately 10% of imaging scans will be re-read by each reader. Unless otherwise specified, the first/original read is what will be used for all reporting and statistical analyses.

8.1. Primary Efficacy Endpoint and Analysis

The primary endpoint is LVEF accuracy. The primary analysis is to demonstrate an improvement in LVEF accuracy from unenhanced imaging to that derived from imaging with DEFINITY® contrast enhancement using CMR as the truth standard.

For each subject, the absolute value of the difference of DEFINITY® LVEF minus CMR LVEF will be calculated. Similarly, the absolute value of the difference of unenhanced imaging LVEF minus CMR LVEF will be calculated for each subject. The primary analysis is to assess the significance of the difference between DEFINITY® and unenhanced echo with respect to the mean “absolute value of the difference versus CMR”.

The null and alternative hypotheses for this study are:

$$H_0: \mu_D = \mu_U \text{ versus } H_1: \mu_D \neq \mu_U; \text{ or, that is}$$

$$H_0: \mu_U - \mu_D = 0 \text{ versus } H_1: \mu_U - \mu_D \neq 0$$

where μ_D and the μ_U are the mean of the DEFINITY® and unenhanced echo absolute value of the difference versus CMR, retrospectively. The null hypothesis will be tested at a two-sided 0.05 level of significance using a paired t-test derived from the sample point estimates of the mean and standard deviation of the difference between unenhanced echo's and DEFINITY's® “absolute value of the difference versus CMR”.

The analyses will be conducted separately for each of the three blinded readers of the DEFINITY® enhanced and unenhanced images. The criterion for success is that the null hypothesis is rejected in favor of DEFINITY® for at least 2 of 3 blinded readers for all subjects. CMR LVEF will be used as the comparator for each of the 3 blinded readers, and is interpreted by a single reader.

The primary analysis will be performed on mITT subjects with non-missing LVEF for DEFINITY®, unenhanced echocardiography, and the truth standard. A supportive analysis will be run where a missing echocardiography or CMR LVEF is multiply imputed using the fully conditional specification (FCS) multiple regression as described in section 6.2.1.

8.1.1. Other Analyses for the Primary Endpoint

The following will be carried out separately for each of the 3 blinded readers without imputation of missing LVEF.

Bias is the mean of the actual (not absolute value) per-subject differences between the imaged LVEF and CMR LVEF. The bias, the two-sided 95% confidence interval (CI) of the bias, the precision (standard deviation of the per-subject differences) and the root mean square error (RMSE) will be calculated for the LVEF derived from the DEFINITY®-enhanced images. The RMSE is the square root of the bias-squared + precision-squared and is considered a measure of overall accuracy. These analyses will be repeated for

This document is confidential.

LVEF values derived from the unenhanced echocardiography versus those from CMR. It is anticipated that the RMSE will be smaller for DEFINITY®-enhanced LVEF than for unenhanced LVEF.

DEFINITY®-enhanced and unenhanced echocardiography LVEF will each be assessed for measurement accuracy against the reference CMR using Bland-Altman analysis and Deming regression analysis. For the Bland-Altman analysis, a plot of the per-subject actual difference between DEFINITY®-enhanced echocardiography and CMR LVEF will be plotted versus the per-subject sum of the two measurements. Limits of agreement (defined as the mean of the DEFINITY® versus CMR difference) ± 2 standard deviations will be shown on the plot. The same analyses will be performed for unenhanced echocardiography using CMR as the reference standard.

Deming regression plots of LVEF versus CMR LVEF will be generated for each of DEFINITY®-enhanced and unenhanced echocardiography. Unweighted Deming regression will be employed to estimate the regression slope and intercept with two-sided 95% CI of each assuming the measurement error is the same for CMR and each of the echocardiography error techniques.

The intra-class correlation coefficient (ICC) and its two-sided 95% CI will be calculated for DEFINITY®-enhanced echo versus CMR and for unenhanced echo versus CMR. The ICCs and their two-sided CIs will be calculated using between and within mean squares from an ANOVA model with method (echocardiography, CMR) and subject as the main effects and LVEF as the dependent variable. The ICC will be calculated using the SAS macro developed by Hamer (1990).

8.2. Secondary Efficacy Endpoint(s) and Analyses

8.2.1. Improvement in accuracy in LVEF assessment using DEFINITY® contrast-enhanced over unenhanced echocardiography in subjects with suboptimal echocardiograms

The primary endpoint analysis will be repeated in the subset of subjects with suboptimal echocardiograms. This will include all primary analyses described in sections 8.1 and 8.1.1, excluding the supportive analyses at the end of section 8.1. The study is not powered to reject the primary endpoint null hypothesis, so the focus is more on the estimate of $\mu_D - \mu_U$, on Bland-Altman plots and on the Deming regression for each blinded reader. There will be no imputation of missing LVEF data for this analysis.

8.2.2. Reduction in inter-reader variability for the assessment of LVEF using DEFINITY® contrast-enhanced versus unenhanced echocardiography

The inter-reader variability among each pair of readers within each imaging modality will be estimated using an intra-class correlation (ICC) and its two-sided 95% CI. The ICC assesses rating reliability by comparing the variability of different ratings of the same subject with the total variation across all ratings and all subjects. The inter-observer variability in the assessment of LVEF between two readers will be determined by percentage of error. The percentage of error will be calculated using the following formula:

$$\text{Percentage of error} = (\text{SD between 2 measurements} / \text{mean of the 2 measurements}) \times 100$$

The mean percentage of error and its 95% CI will be calculated for each pair of readers within each imaging modality. The pairwise ICCs and percentages of error differences will be compared descriptively between contrast-enhanced and unenhanced echocardiography.

In addition, specific to only section 8.2.2, there will also be a separate ICC analysis to assess intra-reader variability as approximately 10% of all echo results will be re-read by each reader.

This document is confidential.

8.2.3. Reduction in inter-reader variability for the assessment of end-diastolic/systolic volumes using DEFINITY® contrast-enhanced versus unenhanced echocardiography

The same analysis used to assess inter-reader variability on LVEF (section 8.2.2) will be conducted for end-diastolic/systolic volumes.

8.2.4. Reduction in inter-reader variability for the assessment of LVEF using DEFINITY® contrast-enhanced versus unenhanced echocardiography in subjects with suboptimal echocardiograms

The same analysis used to assess inter-reader variability on LVEF (section 8.2.2) will be conducted for the subgroup of subjects with suboptimal echocardiograms.

8.2.5. Reduction in inter-reader variability for the assessment of end-diastolic/systolic volumes using DEFINITY® contrast-enhanced versus unenhanced echocardiography in subjects with suboptimal echocardiograms

The same analysis used to assess inter-reader variability on LVEF (section 8.2.4) for the subgroup of subjects with suboptimal echocardiograms will be conducted for end-diastolic/systolic volumes.

This document is confidential.

9. Safety

The population used for safety analyses will be the Safety population (SP). Safety will be assessed on the basis of adverse event (AE) or serious adverse event (SAE) reports, physical examinations, and vital signs.

